5.5. Data Collection

The principal investigator (PI) will ensure that each designee and the scope of the designee's delegated authority are recorded on the Site Signature and Delegation of Authority Log. The designee's signature, initials, start and end dates, list of study related tasks, and document review and approval must be recorded on the form.

5.5.1. Case Report Forms

All Clinical Centers will use electronic data capture (EDC) through an electronic Case Report Forms (eCRF).

An eCRF will be completed for each sample enrolled in the study in order to record relevant demographic, clinical and laboratory information. These forms must be

completed and approved as described in the Study site Manual and as instructed during the training.

Patients whose sample will be included in the study will not be identified by name or by hospital medical record number on the eCRF. A field is available for a study-specific patient identifier code which will uniquely identify each subject. This code will be assigned by a designated individual at the Clinical Center., who is not directly involved in any other aspects of the study. This code will be a series of:

- 5 digit XX-00Y (X being the site number and Y the samples number attributed sequentially)
- And three letters FML: (F being the first letter of the First Name; M being the first letter of the Middle Name or a dash (-) if the persons does not have a middle name; L being the first letter of Last name). As per local regulations, initials can also be a series of three letters determined by clinical center.

This code will have no relation with protected health information, and will be used only to track subject enrollment. A Study Subject Log associating each patient with its patient identifier code will be maintained in a secure location on-site by the designated individual assigning the codes to the patients. Neither the investigator, nor any member of the study team will have access to this log.

Each enrolled sample will be assigned a unique Study Number, which will be identified by bar code labels to be provided by GenePOC. Study Numbers will conform to seven (7) characters in a "GXnnnnA" format: where "G" is a letter identifying the assay (GBS), "X" is a letter identifying the site, "nnnn" is an incrementing number identifying each sample within a study segment, and "A" is a letter denoting the study segment, ("A" for Accuracy or "D" for Discrepant testing). For panel members provided by GenePOC for testing, the same study number pattern will be used and the study segment will be identified as follows: "P" for Proficiency, "R" for Reproducibility and "W" for Workflow Practice.

5.5.2. GenePOC Data

The operator will save the instrument data on properly labeled USB keys on each testing day. On every testing day, data will be uploaded to study specific database.

5.6. Study Materials

5.6.1. Provided by GenePOC

- GenePOC starter kit will minimally contain the following components:
 - GenePOC Instrument
 - GenePOC Sample Racks;
 - GenePOC System User's Manual.
- Tube Vortexer
- Instructions and Training Materials for the Study (*Study Site Manual*);
- GenePOC GBS test IUO kits (including PIE, SBT and DTT);

- CRFs and other required electronic and printed forms;
- Barcode labels with study numbers for all samples and study segments;
- Masked and randomized proficiency panel of characterized samples;
- Shipping materials ice packs, shipping boxes, labels and GenePOC FedEx account number for returning samples, forms, material and equipment, and any other study-required shipping;
- GenePOC Import permit (into Canada) for pathogens (US sites only);
- Freezer boxes, plastic microtubes and screw-caps;
- Sufficient numbers of USB keys for instrument data daily backup;
- Plastic bags to hold/store and ship PIE;
- Swabs for environmental testing;
- Listing for Study binder(s) indicating essential information for archiving purposes at the closing of the study;
- Technical and engineering support as needed;
- Miscellaneous supplies as agreed upon.

5.6.2. Provided by Investigator

- Sample meeting the eligibility criteria outlined in Section 5.3 above;
- Copies of the laboratory's procedures for the GBS collection (if available), routine diagnostic method and quality control;
- Material for routine testing of GBS:
 - Transport media (Amies or Stuart)
 - Lim broth;
 - Blood agar plate (BAP);
 - Tests for identification;
- Facilities, time and personnel necessary to perform the evaluation according to this Study Protocol, and manage the study records according to the Training Manual, the GenePOC instructions and Regulatory Requirements;
- Import permit provided by the CDC (into US only) for pathogens including at least *Streptococcus* genera.
- Trained personnel in the preparation and shipment of biological substances per CDC (USA sites only), Transportation of Dangerous Goods Regulations 14 (TDGR) (Canadian sites only), and IATA guidelines (all sites);
- Incubator at 35-37°C;
- Vaginal/rectal swab;
- All equipment and supplies necessary to perform Reference Method testing, except as noted in previous section;
- Secure room temperature storage space for the GenePOC GBS Assay kits and culture media (as required by package inserts and study Training Manual);
- Adequate refrigerator (between 2°C and 8°C) for the storage of culture media, reference kits (as required by Package Inserts) and fresh samples;

- Adequate storage space in a $-70 \pm 5^\circ\text{C}$ freezer or colder to hold frozen SBT, broths, isolates and panels;
- Control organisms for Reference Method and external control, i.e. *Streptococcus agalactiae* strain (e.g. ATCC 12973);
- Dry ice to send frozen SBT and isolates to GenePOC;
- Site policies or procedures to prevent the release of personal information about patients to the investigator;
- Miscellaneous supplies as agreed upon.

6. LABORATORY TESTING PROCEDURES

6.1. Sample Collection

Vaginal/Rectal swab should be performed in accordance with published guidelines for collection of clinical samples for culture of Group B Streptococcus (CDC in United States and SOGC in Canada).

Samples should be transported to the laboratory according to the hospital's policies but viability of GBS is preserved in transport medium for up to 4 days between 2°C to 25°C .

6.2. Sample Storage and Handling

- Samples that meet the study criteria should be labelled with a bar coded study number provided by GenePOC;
- All relevant information regarding the sample will be recorded on the eCRF; If the sample will be processed within 24 hours, store at room temperature. If the sample will be tested after 24 hours, refrigerate until testing is performed. Sample stored at $2\text{--}8^\circ\text{C}$ can be tested with the GenePOC GBS System and the Reference Method up to 96h of collection.

6.3. Testing Algorithm

Results obtained with the GenePOC GBS System will be compared to those obtained with the Reference Method. All Clinical Centers will be using the same protocol, media and the same Reference Method to ensure uniformity of the test methods across sites. The Reference Method is described in detail in Section 6.3.2 of this protocol.

The vaginal/rectal swab sample will follow the normal hospital path up to the Lim Broth culture, of which an aliquot will be transferred to the GenePOC sample buffer tube (SBT) to be processed with the GenePOC instrument as described in the GenePOC GBS test Package insert. Lim Broth culture remaining in the container will then be used to start the Reference Method.

Lim broth culture must be kept at $2\text{--}8^\circ\text{C}$ after testing for a maximum of five (5) days.

When it is confirmed that no repeat on fresh Lim broth culture is necessary, it will be transferred to a single appropriately labelled tube and frozen at $-70\pm5^{\circ}\text{C}$ or colder for further testing of all negative frozen samples and /or possible future discrepant testing.

The SBTs will be placed at $2\text{--}8^{\circ}\text{C}$ in the event repeat testing is required. If the sample does not require repeat testing, the SBT will be frozen at $-70\pm5^{\circ}\text{C}$.

6.3.1. GenePOC GBS Assay

The GenePOC GBS Assay will be performed according to the assay Package insert.

6.3.1.1. Non-Reportable Results

Samples that initially produce a non-reportable result (Unresolved, indeterminate or External Control failure) will be repeated as described below. Samples that have a reportable (Positive, Negative) result upon repeat testing will be included in the data analyses. Repeated samples that do not give a reportable result will not be included in data analyses. They will be reported separately as non-reportable samples.

6.3.1.1.1. Unresolved Samples (UNR)

An Unresolved Sample is when the internal control fail (no amplification) and the target reaction (GBS) also show no amplification.

An Unresolved sample will be repeated from the refrigerated SBT. These samples may be repeated alone, with other samples to be repeated, or included in a new run with fresh sample. In cases where the sample is Unresolved again, no additional repeat testing will be performed.

6.3.1.1.2. Indeterminate Result (IND)

For an Indeterminate (IND) result due to an instrument failure, testing of the sample(s) will be repeated from the refrigerated SBT and may be tested with other samples that require repeat testing, or included in a new run with fresh samples. For any IND result, the Study Manager should be contacted and the incident must be documented on the eCRF.

6.3.1.1.3. External control failure

In case of a failure of either or both external control, the testing of all clinical samples and any repeated samples included in the run will be repeated from the refrigerated SBTs along with new external control (see Section 6.5 for details). In cases where external control fails again, the Study Manager should be contacted.

6.3.2. Reference Method

The Group B streptococcus bacteria, when present, will be isolated from vaginal/rectal swab samples from pregnant women using a Lim Broth culture and subcultured on Blood agar plate (Important note, only Lim Broth could be used for the study). The swab will be inoculated into a Lim broth (Todd-Hewitt broth supplemented with colistin (10 µg/ml) and nalidixic acid (15 µg/ml)). Incubate inoculated selective broth for 18–24 hours at 35°–37°C in ambient air or 5% CO₂. Subculture the incubated broth on a non-selective blood agar plate (e.g., tryptic soy agar (TSA) with 5% defibrinated sheep blood). After incubation for 18–24 hours at 35°–37°C in ambient air or 5% CO₂, inspect agar plates and identify organisms suggestive of GBS (e.g., large, gray colonies with narrow zone of beta hemolysis). If GBS is not identified after incubation for 18–24 hours, then plates should be reincubated overnight and examine for suspected GBS colonies.

6.3.2.1. GBS Identification

Colonies morphologically resembling GBS from blood agar plate (large, gray, and translucent with a small zone of beta-hemolysis or no zone of hemolysis) will be confirmed as follows:

- Catalase negative;
- Gram-positive cocci in pairs and chains;
- And one of the following positive reactions:
 - Group B streptococcal grouping antisera;
 - Camp test;
 - Rapid hippurate and:
 - PYR test negative if strain is hemolytic (Enterococci can be haemolytic, hippurate positive but PYR positive) or a second previous test if strain is nonhemolytic.

Note: no chromogenic agars could be used as FDA has not cleared any.

6.3.2.2. Inconclusive Result

For an Inconclusive (INC) result in the Reference Method due to a non-interpretable blood agar plate, sample will be retested from the existing inoculated and incubated Lim broth. The Lim broth kept at 2–8°C should be used to inoculate a new blood agar plates as directed in Section 6.3.2.

6.3.2.3. Repeat of negative samples for the Reference Method

In case of suspected irregularity in the testing of the reference method, the entirety of the specimens that gave a negative result with the reference method could be re-tested at a single testing site according to section 6.3.2. In this case, the tested material will be the frozen LIM broth culture stored at -70°C.

6.3.3. Discrepant Testing

Frozen Lim Broth and frozen SBT coming from discrepant result samples will be sent to GenePOC for further testing.

During the course of the trial, the GenePOC Study Manager will inform the sites which samples require to be ship to GenePOC.

6.4. Storage & Shipping

- SBT samples must be kept at 2-8°C after testing for a maximum of five (5) days. When it is confirmed that no repeat is necessary, they will be frozen at -70±5°C or colder for possible future discrepant testing;
- All Lim broths (*Streptococcus agalactiae* isolates) must be stored at -70±5°C or colder, but only samples requested by the Study Manager must be shipped on dry ice to GenePOC;
- All microfluidic cartridges (containing amplified product) must be stored between 2°C to 8°C in a plastic bag and shipped on icepacks to GenePOC as directed by Study Manager.
- Detailed shipping instructions will be provided in the Training Manual.
- At the end of the trial, clinical center will be instructed by Study Manager to destroy, as per their institution policy, samples that did not require shipment to GenePOC.

6.5. Quality Control Testing

In addition to the quality assurance and quality control programs of each laboratory under their respective certification (e.g. CLIA), the minimum quality control described below must be performed during the course of this study.

6.5.1. GENEPOC GBS Assay

6.5.1.1. External Controls

For each day in which samples are processed, appropriate positive and negative external control (ECs) will be tested. These external controls results will need to be kept in the Site File and forwarded to GenePOC.

External control materials are provided by GenePOC. A reference GBS strain bearing the *cfb* gene (e.g. ATCC 12973) will be used as a positive external control (EC) while not inoculated Lim broth will be used as a negative EC.

6.5.1.2. Sample Processing Control

The Processing Control (PC) is incorporated into each microfluidic cartridges and is intended to monitor for the effectiveness of liquid displacement, sample treatment (Lysis) and heating during the sample processing steps. The PC also monitors the integrity of

the PCR reagents, the thermal cycling, and for the presence of inhibitory substances during the amplification and detection steps. A failed PC renders the sample Unresolved.

6.5.1.3. Monitoring for the Presence of DNA Contamination

At the request of the GenePOC Study Manager, the work area and equipment will be monitored for the presence of *Streptococcus agalactiae cfb* gene contamination using the GenePOC GBS test. Should contamination arise, the Study Manager will instruct the site on the measures to take prior to testing additional samples.

6.5.2 Reference Method

As determined by the Laboratory procedure, appropriate positive and negative external control (ECs) will be tested on regular basis for the reference method. These external controls results will need to be kept in the Site File and forwarded to GenePOC.

External control materials are provided by GenePOC. A reference GBS strain bearing the *cfb* gene (e.g. ATCC 12973) will be used as a positive external control (EC) while not inoculated Lim broth will be used as a negative EC.

6.6. Clinical Trial Quality Assurance

The following measures will be taken to assure the quality of the trial conduct and data.

6.6.1. Accountability of investigational Materials

The Clinical Center will account for all GenePOC GBS System investigational materials received from GenePOC. GenePOC clinical trial team will monitor site records for investigational materials accountability. All materials will be handled and disposed of according to Package Insert instructions, Study Site Manual or as directed by the GenePOC Study Manager. Upon completion of the study, all remaining supplies provided by GenePOC will be returned to GenePOC unless otherwise directed by the GenePOC Study Manager in writing.

6.6.2. Process for Protocol Changes and Deviations

6.6.2.1. Protocol Amendment

A Protocol Amendment is a change to, or clarification of, the Study Protocol which may impact the conduct and potential benefit of the study, or participant safety. For each protocol amendment, the GenePOC Study Manager will complete a Protocol Change Form. Protocol changes must be reviewed, approved and signed by the GenePOC Study Manager, a representative of GenePOC and the Principal Investigator. All changes to the Protocol must be submitted to the Clinical Center IEC for examination and approval (if required). The Principal Investigator will ensure that protocol changes are implemented after written approval by all parties (including the IEC if needed), that

all personnel using the protocol at the Clinical Center receive training for the change, and that the new protocol is maintained in the study records at the Clinical Center. Examples of such changes include, but are not limited to: the study objectives, study design, sample sizes, study procedures, or administrative aspects.

6.6.2.2. Protocol Deviations

Each protocol deviation reported to the GenePOC Study Manager by the Clinical Center, observed by the GenePOC Study Manager or CRA during monitoring contacts or visits, or observed through review of CRFs will be documented by the GenePOC Study Manager, CRA or Clinical Center personnel on a Protocol Deviation Form. The Protocol Deviation Form will contain the description of the deviation, the impact on the trial or subject enrollment, the impact to the affected data and any corrective action taken to conform to the protocol. All Protocol Deviation Forms will be reviewed and signed by the GenePOC Study Manager or CRA and either the Principal Investigator (if the Clinical Center was involved or concerned) or the GenePOC Clinical Operations Manager. A copy of each Protocol Deviation Form will be kept at the Clinical Center and the original at GenePOC.

Examples of such deviations include, but are not limited to:

- not completing the testing required by the protocol;
- enrolling inappropriate samples;
- failure to follow Package Insert instructions for use and storage of the investigational device;
- failure to follow the Reference Method (e.g. use of expired materials);
- failure to perform EC as directed;
- not respecting the time to perform testing or retesting.

Protocol deviations might render a data not eligible to be include in the final data analysis.

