2.2. Definitions

Clinical Center(s)	The site(s) that will perform the GENEPOC GBS test and, the culture method for the clinical study.
GENEPOC GBS	Documents provided to investigators by GenePOC including the GenePOC instrument User's Manual, the GenePOC GBS Study Protocol, the GenePOC GBS Package Insert and the GenePOC GBS Study Site Manual.
GENEPOC GBS System	The system is composed of the GenePOC GBS test which is used in conjunction with the GenePOC™ instrument.
PCR Operator	Participating laboratory technician who has successfully completed the proficiency testing
PIE	GBS disposable microfluidic cartridges (describe in this document as PIE because of the shape of the cartridge).
Principal Investigator	Principal Investigator (PI): A person who actually conducts the clinical investigation, under whose immediate direction the test article (device) is used involving a sample derived from a human subject; or, in the event of an investigation conducted by a team of individuals, is the responsible leader of that team.
Reference Method	The Reference Method for this study will be the Culture, a culture method to detect Streptococcus agalactiae strain from a sample.
Sample	Left over Lim broth enrichment intended for regular culture.
Sponsor	GenePOC Inc.
(Patient) sample	Vaginal/rectal swab samples collected for routine laboratory testing from a pregnant woman suspected to be colonized with Streptococcus agalactiae (GBS).

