5.3.1. Inclusion Criteria

- Antepartum pregnant women
- 18 years old and more
- Being at a gestation period of 35 to 37 weeks.
- Vaginal/rectal swab sample
- Transport and storage times, and conditions (e.g. room temperature and/or refrigerated) within the labeled indications.
 - : If the sample will be processed within 24 hours, store at room temperature. If the sample will be tested after 24 hours, refrigerate until testing is performed. Sample stored at 2-8°C can be tested with the GenePOC GBS System
 - Fresh sample must be tested with the Reference Method within 96 hours (4 days) of collection if kept at 2-25°C
- The GenePOC GBS System and the Reference Method will be performed according to the GenePOC GBS Investigation Documents.
- Materials use within their expiration date

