5.3.2. Exclusion Criteria

- Non pregnant women
- Less than 18 years old
- Gestation not between 35-37 weeks
- Transport and storage times and conditions that exceed these Study Protocol requirements
- The GenePOC GBS System and the Reference Method not performed according to the GenePOC GBS Investigation Documents
- Materials used beyond their expiration date
- Samples without all test results required by this Study Protocol. Samples that are inadvertently entered into the study that do not meet the sample inclusion criteria will be made non-compliant.

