5.4. Sample Size Justification

The purpose of the clinical investigation is to enroll sufficient samples from up to four (4) Clinical Centers to obtain a minimum of 150 and a maximum of 160 samples positive for GBS based on the Reference Method final result. With an estimated prevalence of approximately 25%, up to 600 samples could be tested across all Clinical Centers.

A minimum of 30 positive results per site is expected but sites with a higher prevalence of GBS could contribute more positive results to reach the required number. A potential minimum of 200 samples and a potential maximum of 300 total samples will be obtained at each clinical center.

The performance obtained and the statistical confidence intervals will be monitored during the study in order to stop the enrollment when deemed appropriate.

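### Sections 5.3.2 and 6.6.2.2 disagree on whether the same deviations remove a sample, and no masked, locked compliance decision protects the analysis set

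*Combined protocol and SAP*

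**What the plan says.** Section 5.3.2 (Exclusion Criteria) includes "The GenePOC GBS System and the Reference Method not performed according to the GenePOC GBS Investigation Documents", materials past their expiry date, transport or storage outside the limits, and samples lacking a required result. It ends: "Samples that are inadvertently entered into the study that do not meet the sample inclusion criteria will be made non-compliant". Section 5.3.1 makes the same requirement on test performance an inclusion criterion: "The GenePOC GBS System and the Reference Method will be performed according to the GenePOC GBS Investigation Documents". Section 2.2 defines those documents as the instrument manual plus "the GenePOC GBS Study Protocol, the GenePOC GBS Package Insert and the GenePOC GBS Study Site Manual", so the protocol is itself one of them.

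Section 6.6.2.2 (Protocol Deviations) gives an open list of examples: required testing not completed, unsuitable samples enrolled, the package insert not followed, "failure to follow the Reference Method (e.g. use of expired materials"), external controls not run as directed, and testing or retesting out of time. The stated consequence is "Protocol deviations might render a data not eligible to be include in the final data analysis".

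The statistical methods entry in the Protocol Summary bases the analysis on every compliant sample. Section 5.4 says that "The performance obtained and the statistical confidence intervals will be monitored during the study", with a view to stopping enrollment. Under Section 6.3.3, material from discrepant samples goes to the sponsor, and the Study Manager tells sites during the trial which samples to ship.

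**The concern.** Whether a sample is compliant fixes the denominators of sensitivity, specificity and both predictive values. If one section removes a sample for a given event and another only permits its removal, two samples with the same deviation can be handled differently. That matters most if the choice can be made once it is known whether the two methods agreed.

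No bad faith is needed for bias to arise. Discordant samples attract more scrutiny, more scrutiny finds more deviations, and a permissive rule then lets more of those samples leave the analysis. Removing false negatives raises sensitivity and removing false positives raises specificity. Section 9.6.1 says the data will support regulatory submissions, so the sponsor should be able to show that the analysis set was formed without regard to the results.

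**Working it through.** **Step 1. Compare the two sections event by event.**

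| Event listed in 6.6.2.2 (data might be ineligible) | Treatment in 5.3.2 |
|---|---|
| Expired materials in the Reference Method | Listed exclusion |
| Reference Method not followed | Exclusion: test not run per the Investigation Documents |
| Package insert not followed in running the test | Same exclusion; the insert is an Investigation Document |
| Required testing not completed | Exclusion: required results missing |
| Unsuitable sample enrolled | "that do not meet the sample inclusion criteria will be made non-compliant" |
| Testing or retesting out of time | Exclusion if transport or storage limits are exceeded; otherwise through the Investigation Documents criterion |

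For these events one section excludes and the other leaves the matter open.

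**Step 2. Who decides, when, and knowing what?**

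- *Decider.* None is named. Section 6.6.2.2 has each deviation form signed by the sponsor's Study Manager or CRA, together with the Principal Investigator if the site was involved or otherwise a second sponsor role. Signing is not described as ruling on eligibility.
- *Timing.* Section 7.4 has data compliance checked during and after entry, and at least before the final analysis. It does not require this before the two results are compared.
- *Knowledge of results.* Section 5.2.2 masks each method's operators to the other method's result. No masking is stated for sponsor staff. Section 6.6.2.2 allows deviations to be found by reviewing CRFs, and Section 7.1.1 has test results entered in the eCRF.

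**Step 3. Base for an illustration.** Section 5.4 gives at least 150 reference positives at about 25% prevalence: 150 / 0.25 = 600 samples, which reproduces the plan's figure. Reference negatives are then 600 − 150 = 450.

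**Step 4. Effect of one-sided removal.** The documents give no expected accuracy, deviation rate or acceptance limit, so the error counts below are assumptions. Estimate = correct / total. Intervals are exact (Clopper-Pearson) 95%, in line with the exact intervals the plan specifies. Only discordant samples are removed.

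| Assumed case | Before | After |
|---|---|---|
| 8 misses, drop 3 | 142/150 = 94.7% (89.8 to 97.7) | 142/147 = 96.6% (92.2 to 98.9) |
| 10 misses, drop 3 | 140/150 = 93.3% (88.1 to 96.8) | 140/147 = 95.2% (90.4 to 98.1) |
| 10 misses, drop 5 | 140/150 = 93.3% (88.1 to 96.8) | 140/145 = 96.6% (92.1 to 98.9) |
| 15 misses, drop 5 | 135/150 = 90.0% (84.0 to 94.3) | 135/145 = 93.1% (87.7 to 96.6) |
| 18 false positives, drop 5 | 432/450 = 96.0% (93.8 to 97.6) | 432/445 = 97.1% (95.1 to 98.4) |

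**Step 5. Contrast with neutral removal.** Start again from 140/150 and drop 15 positives in proportion, 14 detected and 1 missed. This gives 126/135 = 93.3% (87.7 to 96.9). The estimate does not move. The problem is selection, not exclusion as such.

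**The case against.** The best defence is that the word might is accurate. The list in 6.6.2.2 is open and covers every kind of deviation, including administrative ones such as late data entry. Section 5.3.2 covers only eligibility, storage, materials, test performance and completeness. On that reading some deviations trigger 5.3.2 and others do not, and 6.6.2.2 merely points to the consequence. This stands for deviations outside 5.3.2. It does not resolve the overlapping events: 6.6.2.2 draws no such line, and because the protocol is an Investigation Document, few departures in running either test fall outside 5.3.2.

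There are also controls. Deviation forms record the effect on the data and a copy stays at the site, the database has audit trails, and electronic changes are audited. These make a removal traceable, but they do not hide results from whoever decides it. The Study Site Manual and the post-entry processing documents are not available here and may hold further rules.

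A reader might infer two stronger things. One is that the sponsor alone decides what is excluded. The documents do not say so: no decider is named, and the Principal Investigator co-signs when the site is involved, which would cover most of the listed examples. The other is that selective exclusion is planned or likely. Nothing supports that. Even the sponsor's knowledge of which samples are discordant is an inference, though a fair one, from its role in shipment and performance monitoring.

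**Conclusion.** The concern holds as a gap in protection. For overlapping events the two sections conflict, the outcome sets the primary analysis population, and the protocol states no decider, masking or lock while performance is being monitored. Result-dependent exclusion is therefore not prevented, and it could inflate both sensitivity and specificity.

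In the assumed cases, removing 3 to 5 misses out of 150 reference positives raises sensitivity by about 2 to 3 percentage points, and removing 5 false positives out of 450 negatives raises specificity by about 1 point. These figures show what purely one-sided removal would do. They are not a forecast: no concordant sample is dropped, the error counts are assumed, and the plan gives no acceptance limit that the shift could cross. The conclusion also rests on no further compliance rule existing in the study documents not available here. If one does, the protocol should cite it.

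**What to change.** 1. Align 6.6.2.2 with 5.3.2 through one closed list of objective deviation categories that make a sample non-compliant, and state that other deviations are recorded but do not remove it. Pointing 6.6.2.2 to 5.3.2 as it stands is not enough: the criterion on following the Investigation Documents is so broad that it either excludes every small procedural departure or brings judgement back.
2. Name who decides compliance. Have it decided from a listing with both test results hidden, and lock the decision before the two results are compared. Classify deviations found later from the same masked listing.
3. Report every exclusion by reason and by cell of the 2x2 table.
4. As a supportive analysis, repeat sensitivity and specificity on every sample that has both results.

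The cost is protocol wording, one masked listing and one extra table. Compliance review must also come before results are compared, which needs some coordination because performance is monitored during enrollment and CRF reviewers may see results.
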